#### 9.14.3.3 PET-positivity versus True/False Positivity

Biodistribution parameters in lesions and organs as percentage of mean and max SUV in all lesions, visceral/soft tissue lesions, and bone lesions, lesion-to-background ratio, and lesions size will be used to explore the proportion of participants with participant-level TP and FP at Day 0 and Day 1 by central reader in the Biodistribution Analysis Set. For the summarization of lesions, the mean of the lesions within a participant will be used for the definition.

Biodistribution variables and lesions size will be compared individually between TP vs. FP groups using a Wilcoxon rank sum test at a region-level.

Biodistribution variables will be presented with boxplots for the TP and FP groups.

#### 9.14.3.4 Number of Lesions and Number of Positive Regions on Day 0 vs. Day 1

The total number of, and difference in, the number of lesions detected per participant on the Day 0 and Day 1 Cu-SAR-bisPSMA PET/CT scans will be summarized descriptively by central reader. The number of lesions on Day 0 and Day 1 will be compared using a Wilcoxon signed rank test, with the test p-value and median difference summarized by central reader.

Additionally, the number of positive regions detected per participant on the Day 0 and Day 1 Cu-SAR-bisPSMA PET/CT scans will be summarized descriptively by central reader. The number of positive regions on Day 0 and Day 1 will be compared using a chi-square test, with the test p-value presented by central reader.

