10.4.5.3 Exploratory Efficacy Analyses

The exploratory efficacy endpoints include the following:

- Proportion of participants with any change in intended PC treatment due to either the Day 0 or Day 1 scan;
- Composite CDR, PPV and DR of the Day 0 and Day 1 scan;

- CDR, participant- and region-level PPV and DR of the Day 0 and/or Day 1 scan as a function of baseline variables;
- Relationship between PET-positivity (biodistribution measures such as SUVs and lesion-to-background ratio), versus true/false positivity and as a function of lesion location and size;
- Difference in the number of lesions detected per participant on the Day 0 versus the Day 1 scan;
- Lesion-level overall agreement rate on the Day 0 and Day 1 scans, on the Day 0 and reference scans, and on the Day 1 and reference scans;
- PSA over time and change from baseline;
- PSA velocity and PSA doubling time (PSADT) at the end of the study and at baseline.

Binary exploratory endpoints will be summarized with points estimates and corresponding 2-sided 95% exact binomial CIs based on the FAS.

Difference in the number of lesions detected per participant on the Day 0 versus the Day 1 scan will be summarized descriptively and compared using a paired *t*-test. Other exploratory endpoints including PSA value at each scheduled time point and change from baseline, PSA velocity, and PSADT will be summarized using descriptive statistics.

Descriptive statistics, graphical methods, and statistical modeling as appropriate may be used to explore the relationship between PET-positivity (biodistribution measures such as SUVs and lesion-to-background ratio) and true/false positivity.

In addition, CDR, PPV and DR will also be assessed as a function of the following baseline variables:

- PSA at baseline prior to the scan (<0.5, 0.5 <1.0, 1.0 <2.0, 2.0 <5.0, ≥5);
- PSADT;
- PSA velocity;
- Testosterone at baseline;
- SUV mean and max;
- Lesion-to-background ratio;
- Initial Treatment Received.

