## 3.1.3 Exploratory Study Objectives and Endpoints

Objective	Endpoint		
To evaluate the reproducibility of the  Cu-SAR-bisPSMA PET/CT readings and consistency among readers.	
 
Intra-reader variability per reader.
 
Inter-reader variability expressed by kappa statistics.
 
		
■ To assess the impact of  Cu-SAR-bisPSMA PET/CT on disease management.	
 
Proportion of participants with any change in intended PC treatment due to either the Day 0 or Day 1 scan.
 
		

 
Composite performance of the Day 0 and Day 1 Cu-SAR- bisPSMA PET/CT scans.
 
	Composite CDR defined as the proportion of TP participants on the Day 0 and/or Day 1 scan out of all participants with a Day 0 and/or Day 1 scan.		
	
 
Composite participant/region-level PPV defined as the proportion of TP participants/regions on the Day 0 and/or Day 1 scan out of all participants/regions with a positive Day 0 and/or Day 1 scan.
 
		
	
 
Composite DR defined as the proportion of participants with a positive Day 0 and/or Day 1 scan out of all participants with a Day 0 and/or Day 1 scan.
 
		
■ To determine the effect of baseline variables on the CDR, PPV and DR of  Cu-SAR-bisPSMA PET/CT.	
 
CDR, participant- and region-level PPV and DR of the Day 0 and/or Day 1 scan as a function of baseline variables.
 
		
■ To explore the correlation between  Cu-SAR-bisPSMA PET-positivity and Reference Standard results.	
 
Relationship between PET-positivity (biodistribution measures such as SUVs and lesion-to-background ratio), versus true/false positivity and as a function of lesion location and size.
 
		

September 4, 2024 CONFIDENTIAL Page 13 of 46

- To assess the lesion-level performance of Cu-SARbisPSMA PET/CT.
- Difference in the number of lesions detected per participant on the Day 0 versus the Day 1 scan.
- Overall agreement rate on the Day 0 and Day 1 scans, defined as the number lesions with matching subregion divided by the total number of lesions identified across all scans by either imaging.
- Overall agreement rate on the Day 0 and reference scans, defined as the number lesions with matching subregion divided by the total number of lesions identified across all scans by either imaging.

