#### 8.0 DEVIATIONS FROM PROTOCOL ANALYSES

**Table 3** Deviations from Protocol Analyses

Analysis Endpoint and SAP Section	Protocol v3.0 Original Analysis	Updated Analysis	Rationale
Exploratory Outcome: Function of Baseline	This analysis includes Lesion-to-background ratio as per protocol.	Lesion-to-background ratio not included in this exploratory analysis.	Inclusion of lesion-to- background ratio is not deemed necessary or
Variables Section 9.14.3.2.			informative in this analysis.

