## 9.14.3.1 Composite Cu-SAR-bisPSMA PET/CT Day 0 and Day 1 Results

CDR, participant- and region-level PPV, and DR, as described in the primary and secondary analyses, will be analyzed separately with the proportions derived using the best outcome from both Day 0 and Day 1.

For the composite CDR and PPV a participant or region (if applicable) will be classed as TP if they meet one of the following criteria:

- Classed as TP on Day 0 (regardless of classification on Day 1)
- Classed as TP on Day 1 (regardless of classification on Day 0)

September 4, 2024 CONFIDENTIAL Page 31 of 46

For the composite PPV a participant or region will be classed as FP for the denominator if they meet one of the following criteria and are not classed at TP based on the composite PPV TP criteria above:

- Classed as FP on Day 0 and Day 1
- Classed as FP on Day 0 and classed as either TN, test-negative or non-evaluable on Day 1
- Classed as FP on Day 1 and classed as either TN, test-negative or non-evaluable Day 0

For DR a participant will be classed as having a positive composite Cu-SAR-bisPSMA PET/CT scan if they meet one of the following criteria:

- A positive Cu-SAR-bisPSMA result on both Day 0 and Day 1.
- A positive Cu-SAR-bisPSMA result on Day 0 and negative, missing, or equivocal Cu-SAR-bisPSMA result on Day 1.
- A negative, missing, or equivocal Cu-SAR-bisPSMA result on Day 0 and a positive Cu-SAR-bisPSMA result on Day 1.

The total number of scanned participants (i.e., the denominator for DR) will be the number of participants who underwent a Cu-SAR-bisPSMA PET/CT scan on both Day 0 and Day 1.

The composite CDR, participant- and region-level PPV, and DR will be summarized with 95% Exact Clopper-Pearson CIs for each central reader.

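### Two exploratory Day 0/Day 1 analyses need correcting: an unspecified chi-square test for paired region counts, and a composite detection-rate denominator that contradicts its own definition

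*SAP*

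**What the plan says.** **Region counts.** SAP 9.14.3.4 summarises the number of positive regions per participant on each scan, by central reader, and then states: "The number of positive regions on Day 0 and Day 1 will be compared using a chi-square test". It does not name the form of the test, the unit of analysis or the table. The preceding paragraph of the same section deals with lesion counts from the same two scans: "The number of lesions on Day 0 and Day 1 will be compared using a Wilcoxon signed rank test". In protocol 10.4.5.3 the test for the lesion difference is the *t*-test in its paired form: "will be summarized descriptively and compared using a paired". The protocol gives no test for region counts.

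**Composite DR.** SAP 3.1.3 gives this definition: "participants with a positive Day 0 and/or Day 1 scan out of all participants with a Day 0 and/or Day 1 scan". Protocol Table 3 has the same one. The method in SAP 9.14.3.1 differs. It fixes the denominator in a sentence that begins: "The total number of scanned participants (i.e., the denominator for DR) will be the number of participants who underwent a". That sentence closes by requiring this: "PET/CT scan on both Day 0 and Day 1". The numerator rule in the same section accepts a participant who is positive on one day under this wording: "result on Day 0 and negative, missing, or equivocal". Here the missing or equivocal finding belongs to the second scan, and the mirror case is accepted too. SAP Table 3 has a single row of deviations from the protocol: "Lesion-to-background ratio not included in this exploratory analysis".

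**The concern.** Each participant contributes two region counts from one reader, so the data are paired. An ordinary chi-square test treats the two days as independent samples. Most region statuses should be the same a day later, so that test uses far too large a variance for the difference. Its p-value would sit beside the signed-rank p-value for lesions from the same scans. It could show no difference only because the pairing was thrown away. The comparison bears on the hypothesis in protocol 2.5.1 that delayed imaging may reveal smaller lesions.

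For composite DR, the calculation in SAP 9.14.3.1 is not the endpoint that either document defines, and the change is not declared. If a missing result includes a scan that was never done, a positive participant with one scan enters the numerator but not the denominator. The ratio is then no longer a proportion, it is biased upward, and the planned Clopper-Pearson interval has no basis.

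**Working it through.** The documents give no expected Day 1 gain, no missed-scan rate and no figure for either analysis, so the sizes below rest on stated assumptions. The borrowed planning inputs (protocol 10.3, SAP 4.2) are consistent: 40 × 0.65 × 1.3 = 33.8, about 34 positive regions, and 40/(1 − 0.20) = 50 scanned.

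**1. Region counts: a fixed example.** Assume 50 participants with 0/1/2/3 positive regions on Day 0 in 18/24/6/2 of them (24 + 12 + 6 = 42 regions). Ten gain one region (5 from zero, 4 from one, 1 from two) and two lose one (both from one). Day 1 is then 15/23/9/3 (23 + 18 + 9 = 50 regions).

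- Pearson on the count table: expected counts are 16.5, 23.5, 7.5 and 2.5 per day. χ² = 2 × (1.5²/16.5 + 0.5²/23.5 + 1.5²/7.5 + 0.5²/2.5) = 1.09 on 3 df, p = 0.78.
- Pearson on pooled regions (5 × 50 = 250 per day): 16.8% against 20.0%. χ² = 0.032²/(0.184 × 0.816 × 2/250) = 0.85 on 1 df, p = 0.36.
- Signed-rank: 12 non-zero differences, all of size 1, each with rank 6.5. W⁻ = 2 × 6.5 = 13, mean 12 × 13/4 = 39, variance 12 × 6.5²/4 = 126.75. z = −26/11.26 = −2.31, p = 0.021. Exact: 2 × (1 + 12 + 66)/4096 = 0.039.

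The count-table p-value depends on who gains and who loses; random allocations gave 0.07 to 0.84. The pooled and signed-rank values do not depend on it.

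**2. Region counts: power.** Assumptions: n = 50 and Day 0 counts of 0/1/2/3 in 35/49/13/3%. That gives 65% positive, with (0.49 + 0.26 + 0.09)/0.65 = 1.29 regions each. A stated share gains one region, and 3% lose one where they have one to lose. There were 4,000 simulated trials per row, at the two-sided 5% level.

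| Share gaining | Net regions | Pearson, count table | Pearson, pooled | Signed-rank (normal approx.) |
|---|---|---|---|---|
| 10% | 4 | 0% | 0% | 37% |
| 15% | 6.6 | 0.3% | 0% | 66% |
| 20% | 9.0 | 1.1% | 0.4% | 85% |
| 25% | 11.5 | 2.6% | 4.2% | 94% |
| 30% | 14.1 | 7% | 17% | 99% |
| 40% | 18.9 | 30% | 64% | 100% |
| 50% | 23.9 | 63% | 95% | 100% |

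An exact signed-rank test has less power at small gains: about 20%, 52% and 77% at 10%, 15% and 20%. With no net difference, the two Pearson versions reject 0–0.3% and 0% of the time, and the signed-rank test 3.3–4.7%. With n = 40, the three columns are 0.7/0.3/76% at a 20% gain and 19/42/99.6% at 40%.

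A second model simulated each of the five regions independently, with 17% positive, 80–90% of statuses carried over and 5 points of new positives. Pooled Pearson had 5–9% power, McNemar 60–75% and signed-rank 58–74%.

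**3. Composite DR.** Intervals are Clopper-Pearson. Each row assumes 50 participants with at least one scan, and that missing includes a scan not done.

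| Scanned once (positive) | SAP 9.14.3.1 | And/or definition |
|---|---|---|
| 0 | no difference | no difference |
| 1 (1) | 32/49 = 65.3% | 32/50 = 64.0% |
| 3 (2) | 33/47 = 70.2% (55.1–82.7) | 33/50 = 66.0% (51.2–78.8) |
| 5 (3) | 33/45 = 73.3% | 33/50 = 66.0% |

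An extreme case shows why this is not a proportion: 50 positives, two of them with one scan, give 50/48 = 104%.

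If missing means only a scan done but not read, the numerator lies within the denominator. The both versus and/or mismatch still remains. With 31 positives among 47 scanned twice, the SAP gives 31/47 = 66.0%. The defined endpoint is between 31/50 = 62.0% and 34/50 = 68.0%, depending on the three scanned once.

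**The case against.** On the test, the wording is incomplete rather than plainly wrong. McNemar's test is a chi-square-type test for paired data, so an unpaired test may not be intended. This stands, and the power contrast applies only to the Pearson reading. But McNemar needs binary pairs and these are counts from 0 to 5, so a programmer would have to redefine the unit. A Pearson test here also errs conservatively and cannot manufacture a Day 1 advantage. That is true, but it can hide one.

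On composite DR, the benign reading of missing has support. SAP 7.7 speaks of missing reader results that a backup reader can replace, and the denominator refers to participants who underwent a scan. That supports the unread-scan reading without defining the term, and it leaves the both versus and/or conflict in place. SAP 9.14.1 also provides for participants with no scan at a timepoint. Absence from SAP Table 3 is weak evidence of intent, since that table also omits the change from a paired *t*-test to signed-rank for lesions. The sentence may be a drafting slip, but it is the one that would be programmed.

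The stakes are limited. The region-count comparison is a SAP addition and not a protocol endpoint. SAP 4.1 plans no formal testing, and SAP 9.14 calls its p-values exploratory.

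**Conclusion.** Both points hold. The region-count test is unspecified for paired data, and on its default reading it has almost no power for modest Day 1 gains: about 1% or less against 85% (about 77% exact) when 20% of participants gain a region. The gap closes only when gains are large. Those figures rest on assumed gains, losses and count distribution. The direction does not, provided the two days' results are positively correlated.

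The composite DR denominator contradicts the endpoint definition in both documents. In the examples the estimate shifts by 1.3 points with one single-scan participant and by 7.3 points with five, if missing includes scans not done. There is no shift if all have both scans. Per-day DR and every other primary and secondary endpoint are untouched. These are corrections that should be made, but they do not threaten the trial's main results.

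**What to change.** In SAP 9.14.3.4, compare per-participant positive-region counts between Day 0 and Day 1 with the Wilcoxon signed-rank test, by central reader, as for lesion counts. State whether the p-value is exact or uses the normal approximation.

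In SAP 9.14.3.1, set the composite DR denominator to participants with a Day 0 and/or Day 1 scan, matching SAP 3.1.3 and protocol Table 3. State whether a missing result means a scan not done, a scan not read, or either.

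The cost is two amended SAP sentences. No new data are needed.

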#### 9.14.3.5 Lesion-level Overall Agreement

The following scans will be assessed for overall lesion-level agreement rate per scan type (i.e., bone scan, CT, MRI, PSMA PET, etc.):

September 4, 2024 CONFIDENTIAL Page 33 of 46

- Day 0 vs. Day 1 Cu-SAR-bisPSMA PET/CT scans
- Day 0 Cu-SAR-bisPSMA PET/CT scan vs. SOC Scan for the Day 90 Analysis Visit
- Day 0 Cu-SAR-bisPSMA PET/CT scan vs. SOC Scan for the Day 180 Analysis Visit
- Day 1 Cu-SAR-bisPSMA PET/CT scan vs. SOC Scan for the Day 90 Analysis Visit
- Day 1 Cu-SAR-bisPSMA PET/CT scan vs. SOC Scan for the Day 180 Analysis Visit

Overall agreement rate is defined as the (total number of lesions with matching subregions counted from both scans being analyzed across all patients) / (total number of lesions identified across both scans being analyzed by either imaging across all patients) x 100. All subregions will be used for the agreement rate across all anatomical regions. The overall agreement rate for the comparisons above will be presented by central reader.

If multiple scans of the same type (e.g., bone scans) occur within an analysis window, then the later (i.e. most recent) scan's outcome will be used in the analysis for a given **subregion**. For example, if 2 bone scans occur within the Day 90 Analysis Visit where the first Scan has Subregion X with no unequivocal lesions and second Scan (i.e. most recent scan) has Subregion X with 1 unequivocal lesion, then the value for the Day 90 Analysis Visit is that Subregion X has 1 unequivocal lesion (if the subregion in question is evaluable based on the later scan).

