2.2 Imaging of Prostate Cancer

Conventional imaging modalities such as MRI, CT, and ^{99m}Tc-methylene diphosphonate (^{99m}Tc-MDP) bone scan, suffer from limited sensitivity and specificity, which can result in inaccurate disease staging leading to suboptimal treatment. The use of molecular imaging using PET has therefore been explored to better identify sites of disease. A number of new PET diagnostic radiopharmaceuticals have emerged in the recent years, including agents that accumulate on the basis of alterations in cellular metabolism as well as those that bind to specific proteins, such as PSMA¹³.

Approved diagnostic radiopharmaceuticals that are commonly used to image PC include ^{99m}Tc-MDP bone scan, ¹⁸F-fluorodeoxyglucose (¹⁸F-FDG), ¹⁸F-Sodium Fluoride (¹⁸F-NaF), ¹¹C-choline, ¹⁸F-FACBC (or ¹⁸F-fluciclovine; registered as Axumin[®]), and more recently, PSMA-based PET radiopharmaceuticals, ⁶⁸Ga-PSMA-11 and ¹⁸F-DCFPyL (registered as PYLARIFY[®])^{13,14}.

Currently, ^{99m}Tc-MDP planar whole-body scanning is the imaging standard for detection of osseous metastases. ¹⁸F-Sodium Fluoride uptake mechanism in the bone is similar to that for ^{99m}Tc-MDP but with better sensitivity and specificity in the detection of bone metastases. These scans are both lacking in specificity however, with uptake in areas of bone remodeling such as infection and trauma, in addition to osseous metastases. Furthermore, they are limited in the detection of soft-tissue malignancies, including the primary tumor, lymph node disease, and visceral metastases.

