2.5.1 Imaging Timepoint Selection

The ⁶⁴Cu diagnostic radionuclide has a half-life of 12.7 hours which allows for the completion of PET scans up to at least 24 hours post administration of the radiopharmaceutical.

Preclinical PET/CT images captured at 1, 4 and 24 hours post administration of ⁶⁴Cu-SARbisPSMA showed that the tumor is clearly visible at the 1 hour timepoint. The tumor-tobackground ratio at 4 and 24 hours was much higher than at 1 hour, demonstrating a high degree of accumulation and retention.

For this study, a PET/CT scan completed between 1 and 4 hours post dose of ⁶⁴Cu-SARbisPSMA (Day 0 scan) is considered to be clinically practical and suitable to assess whether ⁶⁴Cu-SAR-bisPSMA is capable of detecting PC in humans. Delayed imaging at 24 hours post dose (Day 1 scan) will also be completed as it is hypothesized that delayed imaging may enable the detection of smaller lesions due to enhanced tumor-to-background ratios following biological clearance of the product over time.

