2.7.3 Exploratory Objectives and Endpoints

The exploratory study objectives and endpoints to be evaluated in this study are presented in Table 3.

Table 3 Exploratory Study Objectives and Endpoints

Objective	Endpoint
To evaluate the reproducibility of the ⁶⁴ Cu-SAR-bisPSMA PET/CT readings and consistency among readers.	Intra-reader variability per reader.Inter-reader variability expressed by kappa statistics.
To assess the impact of ⁶⁴ Cu-SAR- bisPSMA PET/CT on disease management.	Proportion of participants with any change in intended PC treatment due to either the Day 0 or Day 1 scan.

Composite performance of the Day 0 and Day 1 ⁶⁴ Cu-SAR-bisPSMA PET/CT scans.	 Composite CDR defined as the proportion of TP participants on the Day 0 and/or Day 1 scan out of all participants with a Day 0 and/or Day 1 scan. Composite participant/region-level PPV defined as the
	proportion of TP participants/regions on the Day 0 and/or Day 1 scan out of all participants/regions with a positive Day 0 and/or Day 1 scan.
	• Composite DR defined as the proportion of participants with a positive Day 0 and/or Day 1 scan out of all participants with a Day 0 and/or Day 1 scan.
To determine the effect of baseline variables on the CDR, PPV and DR of ⁶⁴ Cu-SAR-bisPSMA PET/CT.	CDR, participant- and region-level PPV and DR of the Day 0 and/or Day 1 scan as a function of baseline variables.
To explore the correlation between ⁶⁴ Cu-SAR-bisPSMA PET-positivity and Reference Standard results.	Relationship between PET-positivity (biodistribution measures such as SUVs and lesion-to-background ratio), versus true/false positivity and as a function of lesion location and size.
To assess the lesion-level performance of ⁶⁴ Cu-SAR-bisPSMA PET/CT.	• Difference in the number of lesions detected per participant on the Day 0 versus the Day 1 scan.
	• Overall agreement rate on the Day 0 and Day 1 scans, defined as the number lesions with matching subregion divided by the total number of lesions identified across all scans by either imaging.
	• Overall agreement rate on the Day 0 and reference scans, defined as the number lesions with matching subregion divided by the total number of lesions identified across all scans by either imaging.
	• Overall agreement rate on the Day 1 and reference scans, defined as the number lesions with matching subregion divided by the total number of lesions identified across all scans by either imaging.

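### The exploratory lesion-level agreement rate ignores unequal lesion counts within a shared subregion, and its all-subregion scope distorts the bone-scan comparison

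*SAP*

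**What the plan says.** The Protocol (2.7.3) sets three exploratory agreement endpoints: Day 0 against Day 1, and each of these against the reference scans. Each is "defined as the number lesions with matching subregion divided by the total number of lesions identified across all scans by either imaging".

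SAP 9.14.3.5 makes this operational. The numerator is the "total number of lesions with matching subregions counted from both scans being analyzed across all patients". The denominator is the "total number of lesions identified across both scans being analyzed by either imaging across all patients". A separate rate is produced for each scan type, with bone scan, CT, MRI and PSMA PET named as examples. On anatomical scope the SAP says: "All subregions will be used for the agreement rate across all anatomical regions".

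Neither document pairs individual lesions or limits the match to the smaller of the two counts. Neither confines a comparison to the anatomy that the comparator images well.

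Two statements elsewhere bear on this. Protocol 2.5.1 says of the Day 1 scan that "it is hypothesized that delayed imaging may enable the detection of smaller lesions". Protocol 2.2 says of the bone agents that "they are limited in the detection of soft-tissue malignancies, including the primary tumor, lymph node disease, and visceral metastases".

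**The concern.** A rate labelled lesion-level should respond when one scan shows lesions that the other does not. Here the thing that has to match is the subregion. Lesions are counted within each subregion (SAP 7.7), and Table 2 of the SAP treats the whole spine, all extremities and the right pelvic nodes as one subregion each. If Day 1 shows more lesions beside one already seen on Day 0, all of them count as agreeing.

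The second problem is scope. A nodal, prostatic or visceral lesion on the study PET enters the bone-scan denominator as a disagreement, although the Protocol itself calls bone agents limited there. The result then depends partly on where the disease lies.

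At stake is the reading of these exploratory endpoints: how far delayed imaging changes the lesion picture, and how far the study PET agrees with each comparator.

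**Working it through.** The documents give no expected value, target or power for this rate, so there is no planned figure to reproduce. The formula was applied directly.

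**Notation.** In one subregion of one participant, n1 and n2 are the lesion counts on the two scans.

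- SAP rate, plain reading: sum of (n1+n2) over subregions with n1>0 and n2>0, divided by the sum of (n1+n2) over all subregions.
- Count-limited rate: sum of 2×min(n1,n2), divided by the sum of (n1+n2).

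Because n1+n2 ≥ 2×min(n1,n2), the SAP rate is never below the count-limited rate over the same subregions. The two are equal only when counts agree in every shared subregion.

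**Day 0 against Day 1, one shared subregion (illustrative counts)**

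| Day 0, Day 1 | SAP rate | Count-limited |
|---|---|---|
| 1, 2 | 3/3 = 100% | 2/3 = 67% |
| 2, 3 | 5/5 = 100% | 4/5 = 80% |
| 1, 5 | 6/6 = 100% | 2/6 = 33% |

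If the 1-against-5 case also has one Day 1 lesion in a new subregion, the SAP rate falls to 6/7 = 86% and the count-limited rate to 2/7 = 29%. So the SAP rate does respond to new subregions.

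**Response to extra lesions.** Write the SAP rate as M/(M+U), with M the lesions in shared subregions and U the rest. Adding k lesions to a shared subregion gives (M+k)/(M+k+U), which is never smaller. For example, take one lesion on each scan in a shared subregion, plus one unmatched Day 0 lesion elsewhere: 2/3 = 67% on both rates. Four more Day 1 lesions in the shared subregion move the SAP rate up to 6/7 = 86% and the count-limited rate down to 2/7 = 29%.

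**Plausible size.** A simulation used 26 positive participants (40 × 65%, from the sample-size section). It assumed on average 1.3 positive subregions each and 1.5 Day 0 lesions per positive subregion. The documents do not give lesion counts. In the last two columns, 20% of participants are given one additional Day 1 lesion at a random site.

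| Mean extra Day 1 lesions per shared subregion | SAP | Count-limited | SAP, with new sites | Count-limited, with new sites |
|---|---|---|---|---|
| 0.25 | 100% | 92% | 96% | 88% |
| 0.5 | 100% | 86% | 96% | 82% |
| 1 | 100% | 75% | 96% | 72% |
| 2 | 100% | 60% | 97% | 58% |

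**Bone scan, scope alone.** SAP Table 2 has 23 subregions: 1+3+3+3 = 10 non-bone and 13 bone. Suppose agreement in bone is perfect (equal counts, same subregions), the bone scan shows nothing outside bone, and a share f of PET lesions is non-bone. The SAP rate is then 2(1−f)/(2−f).

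| f (assumed) | 25% | 50% | 70% | 80% | 90% |
|---|---|---|---|---|---|
| SAP rate | 86% | 67% | 46% | 33% | 18% |

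Within bone only, the same data give 100%.

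**Bone scan, both effects together.** With s non-bone PET lesions, b PET bone lesions and c bone-scan lesions in the same bone subregion, the SAP rate is (b+c)/(s+b+c). The count-limited rate within bone is 2×min(b,c)/(b+c).

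| s, b, c | SAP rate | Count-limited, bone only |
|---|---|---|
| 1, 6, 1 | 7/8 = 88% | 2/7 = 29% |
| 5, 5, 2 | 7/12 = 58% | 4/7 = 57% |
| 20, 5, 2 | 7/27 = 26% | 4/7 = 57% |

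The SAP rate can be too high, about right or too low.

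**The case against.** The strongest case on the other side has four parts.

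*The wording is incomplete rather than wrong.* Min-count matching is not expressly excluded, and SAP 7.8 sends programmatic detail on scan status and reference matching to a supplement not included in the documents. This stands in part: counting every lesion in a shared subregion is the plain reading, not the only possible one. But if the rule is open, two programmers could report 100% or 33% from the same data, so the text still needs to settle it.

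*Evaluability may remove the scope problem.* SAP 9.14.3.5 carries the condition "if the subregion in question is evaluable based on the later scan", and Protocol 7.5.1 leaves interpretation of conventional imaging to the Imaging Review Charter. If soft-tissue subregions on a bone scan were recorded as non-evaluable and dropped, the scope effect would vanish. The condition, however, sits only in the example about repeat scans of one type. The explicit non-evaluable rule in SAP 7.7 is written for the study PET alone.

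*New Day 1 lesions are visible elsewhere.* SAP 9.14.3.4 compares Day 0 and Day 1 lesion numbers per participant, SAP 9.14.2 lists results that differ within subregion, and SAP 9.12 lists the central reads. This limits the harm. It does not correct the rate itself, and 9.14.3.4 does not cover the reference-scan comparisons.

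*The SAP follows the Protocol.* The endpoint is defined there by matching subregion, and a min-count rule would be a different endpoint that still does not prove lesion identity: one lesion in each of two different vertebrae would count as a match. This stands, and is why the existing rate should be kept alongside the new one.

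**Conclusion.** The point holds at minor severity. On its plain reading the SAP rate is never below a count-limited rate over the same subregions and can be well above it: 100% against 33% in the extreme illustration, and 100% against 92% to 60% in the simulation without new sites. The all-subregion scope taken alone lowers the bone-scan rate, to 67% or 33% under perfect bone agreement when 50% or 80% of PET lesions are non-bone. All these sizes rest on assumed counts and shares.

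A reader might infer three stronger things that the documents do not support.

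- That the bone-scan rate always understates agreement. The counting rule pushes the other way, and the net error can take either sign.
- That a bone scan cannot show soft-tissue disease. The Protocol says only that detection is limited.
- That the Day 0/Day 1 rate is bound to look near-perfect and so hide the delayed-imaging hypothesis. Lesions in new subregions lower it, the Protocol does not say that extra lesions will lie beside known ones, and count differences are reported separately.

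The endpoint is exploratory, no formal hypothesis test is planned (SAP 4.1), and CDR and PPV are not affected.

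**What to change.** In SAP 9.14.3.5:

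1. Keep the Protocol-defined rate, but label it *subregion agreement* and state how unequal counts within a subregion are treated.
2. Add a count-limited rate: the sum of 2×min(n1,n2) over the sum of (n1+n2), pooled over subregions and participants. Note that it does not establish lesion identity.
3. For each comparison, use only subregions evaluable on both scans, and Region 5 (bone) only for bone scan.
4. Show matched and total lesion counts beside each rate.
5. Record the change in SAP Table 3, Deviations from Protocol Analyses.

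The work is SAP wording and programming on subregion counts already recorded. The costs are a lower reported Day 0/Day 1 agreement wherever counts differ, fewer lesions in the bone-scan comparisons, and one more documented departure from the Protocol definition.
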